5.2.5.2. Follow-up for Toxicities

Subjects whose study drug is interrupted or permanently discontinued due to an AE or clinically significant laboratory value, must be followed up at the discretion of the investigator until resolution or stabilization of the event, whichever comes first. Clinical experts or specialists, such as, but not limited to, an ophthalmologist, endocrinologist, or dermatologist, should be consulted as deemed necessary. Further guidelines and recommendations for the management of specific infigratinib-induced toxicities (hyperphosphatemia, diarrhea) are provided in [Table 2](#). All subjects must be followed up for AEs and SAEs for 30 days following last dose of infigratinib or until surgery, whichever occurs last.

5.3. Compliance

The investigator or responsible site personnel should instruct the subject to take infigratinib exactly as prescribed to promote compliance. All dosages prescribed and dispensed to the subject and all dose changes or missed doses during the study must be recorded

5.4. Supportive Care Guidelines

5.4.1. Infigratinib Group

Any palliative and supportive care for disease related symptoms, including any medication or therapy for a concurrent medical condition are permitted, except if specifically prohibited below.

Hematopoietic Growth Factors

Hematopoietic growth factors (e.g., erythropoietin [EPO], granulocyte colony -stimulating factor (G-CSF), granulocyte-macrophage colony-stimulating factor [GM-CSF]), and blood transfusions <2 weeks prior to enrollment are not to be administered prophylactically or to be used to meet eligibility criteria. However, these drugs may be administered as per the label of these agents or as dictated by local practice or guidelines established by the American Society of Clinical Oncology (ASCO), ESMO, or other appropriate regional societies.

Management of Hyperphosphatemia

Hyperphosphatemia is a recognized on-target effect of potent and selective inhibitors of the FGFR pathway. While on infigratinib, subjects should avoid foods that are especially high in phosphate and, if possible, should restrict dietary phosphate to 600 – 800 mg/day. High-phosphate foods include dairy products; meats, nuts, and other high-protein foods; processed foods; and dark colas. Prophylactic phosphate binders, started in the evening of first dose of study drug, should be considered (e.g., sevelamer 800 mg three times a day with meals). Subjects who have experienced hyperphosphatemia should take a phosphate binder such as sevelamer, sacroferric oxyhydroxide, lanthanum carbonate, ferric citrate, etc. within 30 minutes of a meal on the day while taking infigratinib. Once the subject has had hyperphosphatemia, the subject should remain on a low phosphate diet, if possible, and take phosphate binder on the days infigratinib is taken, even if the serum phosphorus is normalized. The dose and schedule for phosphate lowering therapy should be in accordance with the package insert, country, or

institutional practice. For patient with GFR 30-49, phosphate binders will be started with first dosing and phosphate levels will be followed every 3 -4 days for the first week of treatment and then phosphate-binder dosage and serum phosphate level monitoring modified depending on serum phosphate levels. An example of a phosphate lowering regimen to manage hyperphosphatemia is provided for consideration below:

- Start sevelamer 800 mg three times a day with meals
- For serum phosphorus >5.5 – 7.0 mg/dL
 - Increase the dose of sevelamer up to 1200 mg every 8 hours
- For serum phosphorus >7.0 – 9.0 mg/dL
 - Increase the dose of sevelamer up to 1600 mg (2 tablets per meal) every 8 hours
 - Consider adding acetazolamide two to three 250 mg tablets per day.

During the infigratinib cycle, subjects do not need to be on a low phosphate diet or take a phosphate binder during their 1-week off period unless serum phosphorus is not normalized.

Management of Diarrhea

Subjects should be instructed to notify their physician immediately at the first signs of poorly formed or loose stool or an increased frequency of bowel movements. Administration of antidiarrheal/anti-motility agents is recommended at the first sign of diarrhea as initial management. Some subjects may require concomitant treatment with more than one antidiarrheal agent. When therapy with antidiarrheal agents does not control the diarrhea to tolerable levels, study drug should be temporarily interrupted or dose reduced per [Table 2](#).

5.5. Prior and Concomitant Medications

At Screening, subjects are to be asked about their history of prior therapies (including prior anticancer therapy); investigators are to check for use of any disallowed prior medications, as outlined in the exclusion criteria for the study (Section [4.2](#)).

All prescription and non-prescription medications administered from the time of first dose of study drug through 30 days after last dose are to be recorded for each subject on the appropriate page of the eCRF. Dates for the start and stop of each concomitant medication are to be recorded, as well as the reason for administration (particularly if administered for an AE). Any changes in dose of concomitant medications are to also be recorded.

Hormone replacement therapies such as thyroid and growth hormones are allowed, as well as estrogen replacement hormone treatment.

5.5.1.1. Permitted Concomitant Therapy Requiring Caution and/or Action

Details for specific medications which require action and/or caution while on study in subjects taking infigratinib are provided in Appendix 1. The rationale for these medications is provided below.

Infigratinib is characterized by pH-dependent solubility, and therefore, medicinal products that alter the pH of the upper GI tract may alter the solubility of infigratinib, and limit bioavailability.

Infigratinib was shown to inhibit the CYP3A4 in *in vitro* assays, thus suggesting an increased risk of drug interactions with concomitant medications that are metabolized by CYP3A4. Infigratinib is a substrate of CYP3A4. Therefore, moderate inhibitors and inducers should be used with caution if an alternative is not available.

Infigratinib was shown *in vitro* to inhibit the drug transporter breast cancer resistance protein (BCRP), with an IC₅₀ of 210 nM. While the clinical relevance of this inhibition is unknown, drugs transported by BCRP should be used with caution.

Anti-emetics are recommended as clinically appropriate at the first sign of nausea and vomiting or as prophylaxis to prevent emesis, along with supportive care according to clinical practice guidelines.

It is recommended to avoid using drugs that are known to cause QT prolongation. Note that some anti-emetics have a known risk for Torsade de Pointes, and therefore need to be used with caution. See Appendix 1 for list of drugs that need to be used with caution. Aprepitant (brand name: Emend) is both a sensitive substrate and a moderate CYP3A4 inhibitor and should be used with caution if an alternative is not available.

Preliminary clinical data have shown that infigratinib has no effect on cardiac conduction or ECG intervals (see current version of the infigratinib Investigator's Brochure). However, medications that have the potential to prolong the QT/QTc interval or induce Torsade de Pointes (possible and conditional risk of TdP/QT prolongation) are allowed with caution. Investigators at their discretion may co-administer such medications, but subjects should be carefully monitored. See Appendix 1 for list of drugs that need to be used with caution. Please note that the list might not be comprehensive.

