5.5.1.2. Prohibited Concomitant Therapy

A concomitant medication is considered prohibited if it appears on any of the prohibited medication lists for any clinical pharmacology property of the drug (e.g., CYP, BCRP).

Details for specific medications prohibited while on study are provided in Appendix 2. The rationale for the restricted medications is provided below.

Other investigational therapies must not be used while the subject is on the study. Anticancer therapy (chemotherapy, biologic or radiation therapy, and surgery) other than the study drug must not be given to subjects while the subject is on study drug. If such agents are required, then the subject must be discontinued from study drug.

Strong inhibitors of CYP3A4 such as the ones listed in Appendix 2 are prohibited because infigratinib is a likely substrate of this isoenzyme.

Strong inducers of CYP3A4 are prohibited because their usage may decrease the exposure of infigratinib. Therefore, agents such as those listed in Appendix 2 are prohibited. Please note that the list may not be exhaustive.

Subjects must also avoid the consumption of grapefruits, grapefruit juice, grapefruit hybrids, pomegranates, star fruits, pomelos, Seville oranges or juice within 7 days prior to the first dose of infigratinib and throughout the treatment period due to a potential CYP3A4 interaction with study drug.

Medications that increase the serum levels of phosphorus and/or calcium are prohibited.

Preliminary clinical data have shown that infigratinib has no effect on cardiac conduction or ECG intervals (See current version of the infigratinib Investigator's Brochure). However, medications that are known to prolong the QT/QTc interval or induce TdP (risk of TdP/QT prolongation) are prohibited. List of these medications is given in Appendix 2. Please note that the list might not be comprehensive.

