12.1. Appendix 1: List of Concomitant Medications

In general, the use of any concomitant medication deemed necessary for the care of the subject is permitted in this study, except as specifically prohibited below. Combination administration of study drugs could result in drug-drug interactions that could potentially lead to reduced activity or enhanced toxicity of the concomitant medication and/or infigratinib.

The following lists are based on the Indiana University School of Medicine's "Clinically Relevant" Table (Flockhart Table™) and supplemented with the FDA draft guidance.

Table 7: Drugs to be used with Caution While on Study

Category	Drug Names
Sensitive CYP3A substrates	afentanyl, alpha-dihydroergocryptine, alprazolam, amlodipine, aplaviroc, aprepitant, aripiprazole, atorvastatin, boceprevir, brecanavir, brotizolam, budesonide, buspirone, capravirine, casopitant, cerivastatin, chlorpheniramine, darifenacin, darunavir, dasatinib, diazepam, diltiazem, dronedarone, ebastine, eletriptan, eplerenone, everolimus, felodipine, fluticasone, imatinib, lovastatin, lumefantrine, lurasidone, maraviroc, midazolam, neratinib, nevirapine, nifedipine, nisoldipine, nitrendipine, perospirone, pimozide, quetiapine, quinine, ridaforolimus, saquinavir, sildenafil, simvastatin, tadalafil, tamoxifen, telaprevir, telithromycin, ticagrelor, tipranavir, tolvaptan, trazodone, triazolam, vardenafil, verapamil, vicriviroc, vincristine
Moderate inhibitors of CYP3A4	amprenavir, aprepitant, atazanavir, cannabinoids, casopitant, cimetidine, ciprofloxacin, darunavir, diltiazem, dronedarone, erythromycin, fosamprenavir, imatinib, metronidazole, Schisandra sphenanthera, sertraline, suboxone, tofisopam, verapamil, zafirlukast
Moderate inducers of CYP3A4	bosentan, cotrimoxazole, efavirenz, etravirine, ethosuximide, genistein, metyrapone, mexiletine, modafinil, nafcillin, ritonavir, talvirinaline, thioridazine, tipranavir
Medications which alter the pH of the GI tract ^{a,b}	antacids, H ₂ antagonists (e.g., ranitidine), proton-pump inhibitors (e.g., omeprazole)

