Medications that have possible risk of TdP/QT prolongation	alfuzosin, amantadine, atazanavir, chloral hydrate, clozapine, dolasetron, dronedarone, eribulin, escitalopram, famotidine, felbamate, fingolimod, foscarnet, fosphenytoin, gatifloxacin, gemifloxacin, gransertron, iloperidone, indapamide, isradipine, lapatinib, levofloxacin, lithium, moexipril, nicardipine, nilotinib, octreotide, ofloxacin, ondansetron, oxytocin, paliperidone, pasireotide, quetiapine, ranolazine, risperidone, roxithromycin, sertindole, sunitinib, tacrolimus, tamoxifen, telithromycin, tizanidine, vardenafil, venlafaxine, voriconazole, ziprasidone

Category	Drug Names
Medications that have conditional risk of TdP/QT prolongation	amitriptyline, amisulpride, ciprofloxacin, clomipramine, desipramine, diphenhydramine, doxepin, fluconazole, fluoxetine, galantamine, imipramine, itraconazole, ketoconazole, nortriptyline, paroxetine, protriptyline, ritonavir, sertraline, solifenacin, trazodone, trimethoprim-sulfa, trimipramine
BCRP substrates	atorvastatin, irinotecan, methotrexate, rosuvastatin, simvastatin, sulfasalazine, topotecan

Abbreviations: BCRP, breast cancer resistance protein; CYP, cytochrome p; FDA, Food and Drug Administration; GI, gastrointestinal; TdP, Torsades de Pointes

^a Infir ritinib should be dosed at least 2 hours before or 10 hours after dosing with a gastric protection agent.

^b If possible, proton pump inhibitors should be avoided due to their long pharmacodynamic effect and replaced with H₂ antagonists or antacids.

Sources: [FDA Guidance for Industry, 2017](#); [Indiana University School of Medicine, 2016](#).

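### Section 5.5.1.1 puts anti-emetics with a known TdP risk under caution while Section 5.5.1.2 bans known QT/TdP drugs, and four drugs, ondansetron among them, are graded both ways in Tables 7 and 8

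*Combined protocol and SAP*

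**What the plan says.** Section 5.5.1.1 covers permitted therapy that needs caution. It recommends anti-emetics at the onset of nausea or vomiting, or as prophylaxis. On QT risk it then says: "It is recommended to avoid using drugs that are known to cause QT prolongation". The sentence on anti-emetics follows directly: "Note that some anti-emetics have a known risk for Torsade de Pointes, and therefore need to be used with caution". The reader is sent to Appendix 1 for the drugs concerned. The next paragraph, on QT-prolonging medication in general, uses a narrower class: "possible and conditional risk of TdP/QT prolongation) are allowed with caution".

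Section 5.5.1.2 covers prohibited therapy and refers to Appendix 2. On the same subject it says: "medications that are known to prolong the QT/QTc interval or induce TdP (risk of TdP/QT prolongation) are prohibited". It also opens with a general rule: "A concomitant medication is considered prohibited if it appears on any of the prohibited medication lists". Appendix 1 carries a matching limit, since a medication needed for the subject's care "is permitted in this study, except as specifically prohibited below". Exclusion criterion 10 (Section 4.2) bars drugs with known QT prolongation or TdP risk in the 7 days before first dose.

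Table 7 (Appendix 1, caution) has one row for possible and one for conditional QT/TdP risk. Table 8 (Appendix 2, prohibited) has a row for established potential.

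**The concern.** These are operative safety instructions, and for drugs with a known QT/TdP risk they disagree. One section treats avoidance as a recommendation and allows caution for anti-emetics. The other prohibits. The tables that sites will consult then grade some of the same drugs as possible risk in one place and established risk in the other.

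The situation is likely to arise. Section 2.4.2 reports nausea in 32.2% of patients in the phase 1 study, and the vomiting rows of Table 2 refer to optimal anti-emetic therapy, so sites will be choosing anti-emetics. A site that reads 5.5.1.1 and follows its cross-reference finds ondansetron among the drugs usable with caution. It has to go to a different section and appendix to learn that the drug is banned. At stake is consistent conduct across patients, and avoidable deviations from a prohibition that the sponsor evidently intended.

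**Working it through.** No sample size, power or error rate is involved. The check is a comparison of the text and a count of shared drug names.

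**Step 1: the instruction for each risk tier.**

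| Tier | Section 5.5.1.1 | Section 5.5.1.2 |
|---|---|---|
| Known risk, any drug | Avoidance recommended | Prohibited |
| Known risk, anti-emetic | Caution, see Appendix 1 | Prohibited |
| Possible or conditional risk | Allowed with caution | Not covered by the QT prohibition |

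Only the third row is free of conflict. The second row also clashes with the third inside 5.5.1.1: if caution is reserved for possible and conditional risk, a known-risk anti-emetic cannot fall under it.

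**Step 2: the QT/TdP rows of the two tables.** Inputs, by count of names: Table 7 possible risk, 46; Table 7 conditional risk, 22; Table 8 established potential, 41.

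- Possible risk ∩ established potential = 4: dronedarone, escitalopram, levofloxacin, ondansetron.
- Conditional risk ∩ established potential = 0.

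The four can be seen in two stretches of Table 7's possible-risk row: "dolasetron, dronedarone, eribulin, escitalopram, famotidine" and "levofloxacin, lithium, moexipril, nicardipine, nilotinib, octreotide, ofloxacin, ondansetron, oxytocin". Each name is also in Table 8's established-potential row.

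**Step 3: separating conflict from redundancy.** By exact spelling, 16 names appear somewhere in both tables, so 16 − 4 = 12 others are shared: erythromycin, fluconazole, itraconazole, ketoconazole, nevirapine, pimozide, ritonavir, saquinavir, tacrolimus, telithromycin, thioridazine and voriconazole. None of the 12 is graded for QT/TdP in both tables. Each is under caution for one property and prohibited for another, which the any-list rule is written to handle. Dronedarone has two further Table 7 entries (sensitive CYP3A substrate, moderate CYP3A4 inhibitor). Those concern a different property and are not part of the QT/TdP conflict. The conflicting Table 7 entries are therefore four.

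**Step 4: what the precedence rules settle.** The four drugs are in Table 8. The any-list rule in 5.5.1.2 and the limit at the start of Appendix 1 both make them prohibited.

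**Step 5: what the rules leave open.** They act on listed drugs and do not alter the sentence in 5.5.1.1, which addresses known-risk anti-emetics as a class. Both sections warn that their lists may be incomplete. For a known-risk anti-emetic on neither list the prose alone decides, and it gives two answers.

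**The case against.** The strongest reply is that the protocol already answers the practical question. Whatever Table 7 says, the four drugs are prohibited by the any-list rule, by the limit in Appendix 1 and by the ban on known QT/TdP drugs. Section 5.5.1.2 comes immediately after 5.5.1.1, so a careful reader meets the ban at once. The anti-emetic sentence can also be read loosely: it follows advice to avoid known QT-prolonging drugs and points to an appendix whose QT rows cover only possible and conditional risk, so known may be a slip.

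Most of this stands, and it is why the point is minor. A reader might infer that the protocol permits ondansetron or the other three drugs. It does not. A reader might also count all 16 shared names as contradictions. The documents do not support that either, because 12 of them differ by property and are covered by the any-list rule.

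The loose reading does not fully rescue the sentence. Its literal words put under caution what 5.5.1.2 bans, and the appendix it cites contains ondansetron. No precedence rule explains why one drug is graded both possible and established for the same property.

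**Conclusion.** This is a minor internal inconsistency in operative safety text, wrong as written. It is confined to the QT and anti-emetic wording in 5.5.1.1 and to four entries in Table 7's possible-risk row. It is an editing fault and not a design decision.

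A reader might infer a demonstrated safety gap, pointing to the few scheduled ECGs. The documents do not support that. Sections 5.5.1.1 and 5.5.1.2 report no infigratinib effect on ECG intervals in preliminary data, Section 8.2.6 allows further assessments when symptoms call for them, and Table 2 has QTcF monitoring and dose-hold rules. How often to record ECGs is a separate question that this correction does not touch. No effect on the primary endpoint, the stopping rule or any statistical figure is claimed.

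The conclusion assumes that the sponsor intends the prohibition, as 5.5.1.2 and exclusion criterion 10 indicate. The counts assume exact spelling: Table 7's afentanyl may be Table 8's alfentanil, which would add one redundant name in the CYP3A rows and leave the four unchanged. That ondansetron is an anti-emetic is general pharmacology and is not stated in the documents.

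**What to change.** Reword the QT and anti-emetic sentences in 5.5.1.1 along these lines: *Drugs with a known risk of QT prolongation or TdP, including anti-emetics, are prohibited (see Appendix 2). Only drugs with possible or conditional risk that are not listed in Table 8 may be used with caution (see Appendix 1).*

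Delete dronedarone, escitalopram, levofloxacin and ondansetron from the possible-risk row of Table 7. As tidying only, dronedarone's two CYP3A entries and the 12 other double-listed names could be removed from Table 7 at the same time.

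The cost is a rewording of part of one subsection and four table deletions at the next amendment, with no effect on data collection or analysis. Anti-emetic options remain in Table 7 that are not in Table 8 (aprepitant, dolasetron, and the entry spelled gransertron).

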5.5.1.2. Prohibited Concomitant Therapy

A concomitant medication is considered prohibited if it appears on any of the prohibited medication lists for any clinical pharmacology property of the drug (e.g., CYP, BCRP).

Details for specific medications prohibited while on study are provided in Appendix 2. The rationale for the restricted medications is provided below.

Other investigational therapies must not be used while the subject is on the study. Anticancer therapy (chemotherapy, biologic or radiation therapy, and surgery) other than the study drug must not be given to subjects while the subject is on study drug. If such agents are required, then the subject must be discontinued from study drug.

Strong inhibitors of CYP3A4 such as the ones listed in Appendix 2 are prohibited because infigratinib is a likely substrate of this isoenzyme.

Strong inducers of CYP3A4 are prohibited because their usage may decrease the exposure of infigratinib. Therefore, agents such as those listed in Appendix 2 are prohibited. Please note that the list may not be exhaustive.

Subjects must also avoid the consumption of grapefruits, grapefruit juice, grapefruit hybrids, pomegranates, star fruits, pomelos, Seville oranges or juice within 7 days prior to the first dose of infigratinib and throughout the treatment period due to a potential CYP3A4 interaction with study drug.

Medications that increase the serum levels of phosphorus and/or calcium are prohibited.

Preliminary clinical data have shown that infigratinib has no effect on cardiac conduction or ECG intervals (See current version of the infigratinib Investigator's Brochure). However, medications that are known to prolong the QT/QTc interval or induce TdP (risk of TdP/QT prolongation) are prohibited. List of these medications is given in Appendix 2. Please note that the list might not be comprehensive.

5.6. Non-drug Therapies

Any significant non-drug therapies (including physical therapy, herbal/natural medications, and blood transfusions) administered from the time of first dose of study drug through 30 days after last dose are to be recorded for each subject on the appropriate page of the eCRF. Dates for the start and stop of each therapy are to be recorded, as well as the reason for administration (particularly if administered for an AE).

Non-drug therapies are prohibited if they appear on any of the prohibited medication lists for any clinical pharmacology or PK property of the drug (e.g., CYP, BCRP) (see Appendix 2.

